**Aim 1:** To examine the effectiveness of a *Stand Up & Move More* intervention to reduce sedentary behavior, increase physical activity, and improve functional performance and quality of life in older adults. *Working Hypothesis:* It is hypothesized that there will be significant reductions in the primary outcome of sedentary behavior and increases/improvements in the secondary outcomes of physical activity, functional performance and health-related quality of life in the intervention group compared to no significant changes in the wait-list control group.

**Aim 2:** To examine the feasibility of implementing a *Stand Up & Move More* intervention by State Aging Units to underserved communities in the state. *Working Hypothesis:* It is hypothesized that the intervention to reduce sedentary behavior will be feasible to implement by State Aging Units to older adults in underserved communities.

The intervention we are proposing to test statewide was developed with community collaborators. Sitting less seems simple but intervention is required to get older adults to do it. If breaking up sitting time by standing up and moving more throughout the day proves to be effective then we will have identified a **practical** intervention with the potential to improve the health and function of older adults that could be translated to communities across the country.

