## RESEARCH DESIGN AND METHODS

Previous Research: With funding from the Greater Wisconsin Agency on Aging Resources, research was conducted to develop an intervention to reduce sedentary behavior and examine the feasibility of implementing the intervention by a State Aging Unit in a community setting. The research was conducted in two communities in Rock County, Wisconsin which is made up of

small urban and rural communities. The older adults in these communities had high levels of sedentary behavior (averaging almost 11 hours of their waking hours per day sitting) and their function scores were below the population average. A 4-week intervention based on self-regulation theory and designed to break up extended sitting time by standing up multiple times during the day significantly ( $p < 0.05$ ) reduced sedentary behavior (60 min/day), was associated with moderate increases in light intensity physical activity (effect size = 0.52; 35 minutes/day), and large effect size improvements in mobility (i.e., gait speed; effect size = 0.74) as well as vitality (effect size = 1.15). Importantly, reductions in sedentary behavior were sustained 4 weeks after the intervention ended. Strategies used most often included standing up during television commercials, and spreading household chores out across the day. Additional strategies included getting up to get a drink of water, and setting a timer to stand up. Twenty participants (out of a total of 25) completed the 4-week program and 90% of the participants expressed high satisfaction with the program (e.g., “What a great program. It made me realize how much I sit during the day and helped me manage my sitting time”). Also, participants indicated that breaking up sitting time was more appealing to them than increasing exercise. Further, the intervention was found to be feasible for staff to implement. The director of the Rock County Council on Aging who led the workshops stated “The intervention worked because it was simple. It is not complex and that is the beauty of it.” Thus, our pilot results are quite promising and represent the development, preliminary feasibility, and piloting stages of the *Stand Up & Move More* intervention in a small sample of older adults.

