**Design:** As a next step, a randomized controlled trial will be conducted with a larger sample of older adults from underserved communities. Older adults from 4 counties in Wisconsin (i.e., Dane, Iowa, Rock & Vilas) will be randomized into intervention or wait-list control groups (Note: a block randomization scheme will be used blocking for age). Our pilot data suggests an intervention design of one session per week for 4 weeks with a refresher session at 8 weeks is feasible and likely to sustain behavior change. The primary outcome measure is sedentary behavior while the secondary outcome measures include physical activity, functional performance, and health-related quality of life. Assessments will be completed at baseline, after the intervention (4 weeks) and at follow-up (at 12 weeks as suggested by our community partners as being a reasonable time for the older adults in the control group to wait for the next workshop to begin). Feasibility of implementing the intervention will be assessed via semi-structured interviews of the health program facilitators, while feasibility of completing the *Stand Up & Move More* program by older adults will be assessed by program adherence and participant satisfaction.

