**Participants:** A power analysis was performed to estimate optimal sample size for detecting potential differences between intervention and wait-list control groups in sedentary behavior using a repeated measures design, with an alpha of 0.05, a power of 0.80, and a medium effect (0.57). Results from the G-power analysis indicated a total of 68 participants (34 per group) would be needed for the proposed study but we have increased sample size in anticipation of a potential attrition rate of approximately 20% (a minimum of 80 adults older than 55 yrs will be recruited). Four counties (Rock, Iowa, Vilas & Dane) will each recruit between 20–30 older adults who will be randomized to either the intervention group ( $n = 10–15$ ) or the control group ( $n = 10–15$ ). Inclusion criteria includes > 55 yrs, currently inactive or low active (i.e., < 60 min of physical activity/week), residents of Rock, Iowa, Vilas or Dane Counties, and residing in a home or an apartment. Exclusion criteria are low levels of sedentary behavior (i.e.,  $\leq 6$  hours/day); recent hospitalization (past month); uncontrolled medical conditions including uncontrolled hypertension (BP > 170 systolic or 100 diastolic), heart disease (symptoms of angina with minimal exertion in the past month), actively receiving chemotherapy or palliative care for cancer, stage 4 liver disease (e.g., cirrhosis with ascites or encephalopathy or history of

bleeding esophageal varices), end-stage renal disease (on dialysis or creatine > 4), or end-stage pulmonary disease (dyspnea at rest or with minimal exertion); severe arthritis or any orthopedic condition that could be made worse by standing up and moving more; inability to stand up without assistance of another person; and inability to speak or hear spoken English. Participants will be given a gift card up to \$50 upon study completion (\$20 for participating in the study plus \$10 per each of three assessments).

Recruitment of Participants: Staff from Aging Units in the four counties will recruit older adults from their counties for this study. Recruitment strategies include announcements in senior newsletters, at congregate dining sites, churches, and medical clinics. In addition, announcements will be posted on Aging Unit websites, and flyers will be sent to mailing lists of older adults in the various counties. These strategies were used in our pilot research and worked well in recruiting the estimated sample size.

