*\*Note:* [name], our community research associate, will provide the training and fidelity monitoring of our community partners. She has been involved in statewide coordination of evidence-based health promotion programs for older adults in Wisconsin for over 9 years. Part of her responsibilities have included training, overseeing, and fidelity monitoring for health promotion programs (e.g., the “Chronic Disease Self-Management” program). In addition, [name] (co-investigator) has expertise in developing tools for fidelity monitoring for the health promotion program “Stepping On.” These fidelity tools are used nationally to ensure high fidelity with dissemination of falls prevention programs. Treatment fidelity implementation in the proposed study is consistent with NIH Behavior Change Consortium Treatment Fidelity Workgroup recommendations involving study design, training of providers, delivery of treatment, receipt of treatment, and enactment of treatment skills.

**Wait-List Control Group:** Older adults assigned to the control group will be instructed to go about their daily routines during the first 12 weeks of the study. They will complete, in the same manner as the intervention group, assessments at baseline, 4, and 12 weeks. The control participants will receive the *Stand Up & Move More* intervention after 12 weeks.

**Measures:** Data collection sessions will be held the week prior to beginning the intervention (at the introductory meeting), at 4 weeks (following the delivery of the intervention), and at 12 weeks (follow-up) at readily accessible sites in each county (see Appendices for a summary table of outcomes assessment). Assessments will be completed by assessors trained by [name]. The assessors will be blinded to group assignment, and every effort will be made to ensure the assessors remain blinded throughout the duration of the study.

**Sedentary behavior** will be assessed both subjectively and objectively: **(a)** Participants will be interviewed by the investigators about their time spent sitting during the day in different activities (e.g., watching TV, reading) over the past week using a previously validated questionnaire for older adults; **(b)** Activity Monitors will be worn at each assessment for one week: The *activPAL*

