*Demographic and Health History Questionnaire*: At baseline, participants will be asked to complete a questionnaire regarding health status and demographic information (date of birth, sex, race, ethnicity, education, and marital status), current physical activity, smoking status, and current alcohol intake.

*Mediators of Behavior Change*: As suggested by NIH reviewers, we have added selected mediators of behavior change. Participants will complete questionnaires assessing self-regulation strategies, self-efficacy, and outcome expectancies.

*Adherence to the Intervention and Outcome Assessments*: Adherence to the *Stand Up and Move More* intervention workshop will consist of participants attending at least 50% of the sessions. As for outcome assessments, adherence to wearing the accelerometers will be defined as wearing the monitors 4 out of 7 days.

*Analyses*: The primary sedentary behavior outcome variables include total sedentary time, time spent sitting in long bouts (i.e.,  $\geq 60$  minutes), and sit-to-stand transitions as measured by the activPAL. These outcomes will be examined adjusting for monitor wear time if wear time differs between groups. We will also be able to analyze changes in specific domains of sedentary behavior (e.g., watching TV, reading) from data obtained from the sedentary behavior questionnaire. A 2 (groups) x 3 trials (pre, post-1, and post-2) repeated measures ANOVA will be used to examine differences between groups in changes in sedentary behavior before and following the intervention and control conditions. Similarly, for the secondary variables of physical activity, functional performance, health-related quality of life, and mediators of behavior change, a series of 2 x 3 repeated measures ANOVA's will be performed. Significant main effects and interactions will be assessed with planned contrasts. Effect sizes will be calculated to examine the magnitude of differences between groups as well as the magnitude of change from pre to post-intervention according to methods described by Cohen. In addition,

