correlational analyses will be performed to examine the relationship between sedentary behavior and the secondary outcomes. Significance will be set at  $p < 0.05$ . {Note: since sample size was estimated for our primary outcome variable of sedentary behavior, we recognize the potential limitation of our sample for secondary outcomes. However, if one or more of the secondary outcomes shows a trend in the direction of significance and/or shows a moderate to large effect size, the number of participants can be expanded in subsequent research to address a specific hypothesis}.

*Note:* Multiple imputation will be used to account for missing data (and attrition) under a missing-at-random assumption using MICE package in R. Longitudinal models for the outcomes at the two post-intervention visits will adjust the pre-intervention value as a covariate and explicitly model changes in the outcomes over time. Intervention workshop will be included in the included model as a random effect to account for correlations in outcomes between subjects in the same workshop.

Feasibility: The feasibility of implementing the program by our community partners will be assessed after the refresher session (at 8 wks) via semi-structured interviews. The Aging Unit Directors and Health Program Facilitators will be interviewed and asked about their satisfaction with the intervention, the ease and difficulty of implementing the program, and their likelihood of sustaining the intervention outside of a research study {*Note: Aging Units offer evidence-based health promotion programs to older adults in their counties which are funded by the Older Americans Act (OAA). When a new health promotion program is shown to be evidence-based (i.e., effective, translatable), Aging Units can use OAA funding to support and sustain implementation of the program*}. Interviews will be transcribed and coded, classified, and organized into main themes using thematic analyses. Feasibility of completing the program by older adults will be assessed after the refresher session (at 8 wks) on the basis of program adherence (i.e., attendance) and participant satisfaction (brief questionnaire).

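### Three activPAL variables are primary at p<0.05 with no success rule; if any one may carry Aim 1, a false claim of benefit has about a 5.4-6.7% chance under assumed correlations, not 2.5%

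*Combined protocol and SAP*

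**What the plan says.** Most of the document speaks of a single primary outcome. Aim 1 predicts that "there will be significant reductions in the primary outcome of sedentary behavior". Design states: "The primary outcome measure is sedentary behavior while the secondary outcome measures include physical activity". The power paragraph under Participants is for "detecting potential differences between intervention and wait-list control groups in sedentary behavior using a repeated measures design", with alpha 0.05, power 0.80 and an effect of 0.57, giving 68 participants (34 per group). The note under Analyses refers back to this in the singular: "since sample size was estimated for our primary outcome variable of sedentary behavior".

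Analyses then sets out more than one variable: "The primary sedentary behavior outcome variables include total sedentary time, time spent sitting in long bouts", where a long bout is 60 minutes or more, followed by sit-to-stand transitions. All three come from the activPAL. The test is a two-group by three-occasion analysis: "repeated measures ANOVA will be used to examine differences between groups in changes in sedentary behavior". Significance is set at 0.05. No section gives a testing order, an adjustment, a lead variable or a rule for how many of the three must succeed. The note's caution about limited sample size covers secondary outcomes only.

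**The concern.** With three primary variables each tested at 0.05, the meaning of a positive trial depends on a rule that the plan does not contain. Three rules fit the text equally well: any one variable is enough, some subset is enough, or all three are needed. They have different error rates and different power.

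Under the first rule, Aim 1 could be declared met on whichever variable happened to reach significance, and the error of that claim would exceed the nominal level. Under the last, the claim is conservative, but the trial was not sized for it. The choice would in effect be made after the results are known. This matters beyond the trial, because the Feasibility section says that a program shown to be evidence-based can be supported with Older Americans Act funds.

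**Working it through.** **Inputs from the documents.** Three primary variables (Analyses); threshold 0.05 (Analyses); alpha 0.05, power 0.80, effect 0.57 and 68 participants (Participants).

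**Inputs assumed.** Sidedness is not stated; the planned F tests are non-directional, so 0.05 is read as two-sided, which leaves 0.025 in the favourable direction. No correlations between the three variables are given, so ranges are shown. Transitions are signed so that more is favourable.

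**Step 1: the plan's own figure.** Read 0.57 as a standardised mean difference, so f = 0.57/2 = 0.285. For the between-groups test over m = 3 occasions with assumed correlation 0.5 between occasions, the noncentrality is f² × N × m / (1 + (m − 1) × 0.5). At N = 68 this is 0.285² × 68 × 3 / 2 = 8.28. Power is 0.810, and N = 66 gives 0.798. So 68 is reproduced at unadjusted alpha 0.05 for one outcome and contains no allowance for three tests. This rests on the assumed 0.5 and on the between-groups test; other readings that were tried do not give 68.

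**Step 2: any one of three, independent variables.** Two-sided: 1 − 0.95³ = 14.3%. Favourable direction only: 1 − 0.975³ = 7.3%, against 2.5%.

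**Step 3: any one of three, correlated variables.** With no true effect on any variable, take three standard normal statistics with the stated correlations. Find the probability that at least one exceeds 1.96 in absolute value (two-sided) or exceeds +1.96 (favourable). Simulation used 2,000,000 draws per case.

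| Assumed correlation | Two-sided | Favourable only |
|---|---|---|
| 0, all pairs | 14.3% | 7.3% |
| 0.5, all pairs | 12.5% | 6.3% |
| 0.7, all pairs | 10.9% | 5.5% |
| 0.9, all pairs | 8.4% | 4.2% |
| 0.7-0.9 between the two time variables; -0.2 to 0.5 with transitions | 10.9-12.9% | 5.4-6.7% |

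The last row is the more realistic structure: long-bout time is part of total sedentary time, while transitions count events. Repeating the equal-correlation cases with 2-df tests, as for a group-by-time interaction, gives nearly the same two-sided range (8.6-14.2%).

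**Step 4: only the two time variables count.** Any one of two at correlation 0.9 down to 0.7 gives 7.0-8.4% two-sided and 3.5-4.2% favourable.

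**Step 5: all three required.** The error cannot exceed that of any single test. It is 0.3%, 0.9% and 2.3% two-sided at equal correlation 0.5, 0.7 and 0.9. The cost is power: if each test had the 0.81 of Step 1 and the three were independent, joint power would be 0.81³ = 0.53. Positive correlation raises this, but not above 0.81.

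**Step 6: fixed order.** Nothing is claimed unless the first test succeeds at 0.05, so the error is 5.0% at any correlation.

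**The case against.** The strongest reply is that the any-one-of-three rule is an assumption. The plan is silent; it does not grant permission to claim success on one variable. That stands, and the inflated rates are conditional on that rule. A reader might infer that the trial's error simply is 14%. The documents do not support this: that figure needs zero correlation, although one time variable is contained in the other, and it counts significant worsening, which nobody would report as benefit.

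A second reply is that total sedentary time is plainly the intended primary variable. It is listed first, Aim 1 predicts reductions, and the pilot result under Previous Research is in minutes: "reduced sedentary behavior (60 min/day), was associated with moderate increases in light intensity physical activity". A reader might infer that the choice is already made. Other text points elsewhere. The Background describes helping people interrupt extended sitting by standing up repeatedly. The Intervention section targets sitting of an hour or more and sets goals as extra breaks per day, rising from 3-5 to 10-12. Measures gives the activPAL two purposes, sedentary time and the count of interruptions. Nor does Participants tie the 0.57 to any one variable.

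A third reply is that these are three facets of one construct from one device in a trial of about 80 people. High correlation does reduce the inflation, but even at 0.9 for every pair the two-sided rate is 8.4%.

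Finally, clustering by workshop and the interim analysis without a numerical boundary might seem to make this worse. They are separate points. They do not enter the figures here and add no weight to this one.

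**Conclusion.** The point holds in conditional form. The plan names three primary variables and does not fix what counts as success on Aim 1, while its sample size allows for one test.

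If any one variable may carry the claim, the chance of a false claim of benefit is about 2.2 to 2.7 times nominal (5.4/2.5 to 6.7/2.5) under the more realistic correlations. The outer range over equal correlations from 0.9 down to 0 is 4.2-7.3% favourable, or 8.4-14.3% two-sided. If only the two time variables count, the excess is smaller. If all three must succeed, there is no inflation, but the power paragraph does not cover that claim.

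All correlations are assumed, and the calculation uses one test per variable at one final analysis. The absence of a rule is certain from the text; the size of its effect is not. It should be corrected because the rule decides the trial's main conclusion.

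**What to change.** In Analyses, before any unblinded data are seen, do one of the following:

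- name one of the three as the single primary variable and make the other two secondary;
- keep all three and test them in a stated fixed order, each at two-sided 0.05 and only if the one before it is significant; or
- keep all three and apply Holm.

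Total sedentary time is a reasonable lead given the pilot result, but the stated targets of the intervention also support long bouts or transitions, so the sponsor should choose. Apply the rule to one named group comparison from one named model, since Analyses describes both a repeated measures ANOVA and a baseline-adjusted longitudinal model. In Participants, state which variable the 0.57 refers to. Make the singular wording in Aim 1 and Design agree.

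The cost is mainly wording. Variables not chosen, or placed later in the order, cannot on their own support the primary claim. A fixed order splits no alpha. Holm does cost power: its first step is at 0.05/3 = 0.0167, where the model that reproduces 68 gives power 0.66 for a single variable instead of 0.81.

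### The primary sedentary outcomes are given two different analyses with no order of precedence and no deciding visit, and one of them (the ANOVA) omits the workshop correlation that the other allows for

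*Combined protocol and SAP*

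**What the plan says.** The Analyses section opens with the outcomes: "The primary sedentary behavior outcome variables include total sedentary time, time spent sitting in long bouts", plus sit-to-stand transitions, all from the activPAL. For testing it says: "A 2 (groups) x 3 trials (pre, post-1, and post-2) repeated measures ANOVA will be used to examine differences between groups", the differences being in change in sedentary behavior. The follow-up rule is: "Significant main effects and interactions will be assessed with planned contrasts". The contrasts are not listed. The secondary outcomes and mediators get the same ANOVA.

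The Note at the end of the section reads differently. It says "Multiple imputation will be used to account for missing data (and attrition) under a missing-at-random assumption", and then: "Longitudinal models for the outcomes at the two post-intervention visits will adjust the pre-intervention value as a covariate". It adds: "Intervention workshop will be included in the included model as a random effect", with the stated purpose "to account for correlations in outcomes between subjects in the same workshop".

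Three other places matter:
- **Measures**: baseline is taken the week before the intervention begins.
- **Wait-List Control Group**: controls receive no workshop during the first 12 weeks.
- **Potential Problems and Alternative Strategies**: each of the four counties runs one intervention workshop and one wait-list workshop, so four intervention workshops are planned.

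**The concern.** Both statements are current text and both apply to the primary outcomes, but they are different models. In the ANOVA, baseline is a response and participants are treated as independent. In the Note's model, baseline is a covariate and workshop members may be correlated. No sentence says whether the Note replaces, supplements or ranks below the ANOVA, and no visit or average is named as deciding.

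Two things are at stake. First, with two models and several possible contrasts at p < 0.05, the deciding result can be chosen after all of them have been seen. Second, if the ANOVA decides, its error rate depends on a correlation that the plan anticipates but that this test leaves out. Correlation produced by a workshop arises after baseline, so it does not cancel when change is compared.

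**Working it through.** **Inputs from the documents.** Alpha 0.05, power 0.80, effect 0.57, 68 evaluable (34 per group), at least 80 recruited and about 20% attrition (Participants); 10–15 per workshop (Intervention to Reduce Sedentary Behavior); four intervention workshops. With 20% attrition, 80 × 0.8 = 64 are analysed, or about 8 per workshop of 10.

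**Assumptions not in the documents.** 0.57 is a standardised mean difference d, the same at both post visits; correlation ρ = 0.5 between visits; workshop effect in the intervention arm only; ICC 0 to 0.10.

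**1. The plan's own figure.** The G*Power between-factors formula is λ = N f² m / (1 + (m − 1)ρ). With f = 0.57/2 = 0.285 and m = 3, λ = 68 × 0.081225 × 3 / 2 = 8.285 and power is 81%. So 68 is reproduced, but as the group main effect averaged over three visits *including baseline*, with no clustering. That is neither a comparison of change nor the Note's model.

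**2. The candidate tests are not interchangeable.** Take n = 34 per group, mean differences (0, d, d) and no workshop correlation:
- Group main effect: difference 2d/3 = 0.38, variance (1 + 2ρ)/3 = 0.667; noncentrality 0.38/√(2 × 0.667/34) = 1.92; power 47%.
- Group-by-time interaction: λ = (n/2) × (2d²/3)/(1 − ρ) = 17 × 0.2166/0.5 = 7.36; power 67%.
- Average of post visits minus baseline (change contrast): variance (1 + ρ)/2 + 1 − 2ρ = 0.75; noncentrality 0.57/√(2 × 0.75/34) = 2.71; power 76%.
- Baseline-adjusted week 12: variance 1 − ρ² = 0.75; power 76%.
- Baseline-adjusted post average: variance (1 + ρ)/2 − ρ² = 0.5; noncentrality 0.57/√(2 × 0.5/34) = 3.32; power 91%.

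For interaction / change contrast / baseline-adjusted average, power is 64/74/89% with 64 analysed and 75/83/95% with 80.

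**3. Type I error of the ANOVA.** Let ICC be the workshop share of total variance at each post visit. A workshop effect common to both post visits gives change scores a within-workshop correlation of ICC/0.75 in the intervention arm and none in the control arm. The variance of the group difference is then understated by a factor DE = 1 + (m − 1) × ICC/(2 × 0.75), where m is now workshop size. The error is about 2 × (1 − Φ(1.96/√DE)). For m = 10 and ICC 0.05, DE = 1 + 9 × 0.05/1.5 = 1.30, which gives 8.6%. Simulated values beside this approximation:

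| Workshop size | ICC | Interaction (simulated) | Change contrast (simulated) | Change contrast (formula) |
|---|---|---|---|---|
| 8 | 0.05 | 7.0% | 7.7% | 7.8% |
| 8 | 0.10 | 8.8% | 9.9% | 10.6% |
| 10 | 0.05 | 7.3% | 8.4% | 8.6% |
| 10 | 0.10 | 9.4% | 12.0% | 12.1% |
| 15 | 0.05 | 8.4% | 10.6% | 10.6% |
| 15 | 0.10 | 14.2% | 16.8% | 15.9% |

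At ICC 0 the simulated error is about 5%; at ICC 0.01 it is 5.4–6.1%. Separate simulations agree within about two percentage points.

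**4. What the workshop term costs.** These simulations put ICC on the baseline-adjusted scale, where the same value stands for a smaller workshop variance than in step 3. The mixed model uses Satterthwaite degrees of freedom and four workshops. Power at ICC 0 / 0.05 / 0.10:
- 64 analysed: 80/71/62%, against 74/72/71% for the ANOVA change contrast.
- 80 analysed: 88/78/67%, against 83/80/79%.

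The order reverses near ICC 0.05, partly because the ANOVA figures come from a test whose error exceeds 5%.

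**The case against.** The best defence is that the Note is the operative text. It says what the models will do, it covers the outcomes generally, and on that reading workshop correlation is handled and the ANOVA sentence is a leftover. This is a fair reading, and it rules out the inference that the plan simply ignores clustering. But the Note does not say that it replaces the ANOVA, and it names no deciding visit.

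A reader might also infer that the ANOVA's type I error is certainly above 5%. The documents do not support that, because they give no ICC. Participants are individually randomised, and if workshops affected nobody the 5% level would hold; inflation needs workshop effects that vary around a zero mean. At ICC 0.01 the excess is small. Correlation already present equally at baseline would leave the interaction test at its level (4.9% in simulation).

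Two further points stand in part. The ANOVA text targets differences in change, which points to group-by-time, so the estimand is not wholly open; the deciding visit or average is what is missing. And the Note's reference to the intervention workshop already leans towards a term for intervention participants only, although the coding of controls is left unsaid.

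**Conclusion.** The conflict holds on the text alone and needs no assumption: two current, non-equivalent analyses of the primary outcomes, no ranking, and no deciding visit or average. It should be settled before the data are analysed.

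The error-rate point is conditional. If workshop members become correlated after baseline, the ANOVA's type I error can exceed 5%: about 7–10% with workshops of 8, 7–12% with 10 and 8–17% with 15, at total-variance ICC 0.05–0.10. These ranges run from the interaction to the change contrast and rest on the stated assumptions about correlation, number of workshops and a one-arm effect.

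It would be tempting to add that the Note's model is also the more powerful one. That is clear only when workshop correlation is absent or small. The reason to prefer it is error control and agreement with the correlation that the plan expects.

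**What to change.** Required wording:
- Name the Note's baseline-adjusted longitudinal model of weeks 4 and 12 as the governing analysis. Apply the workshop random effect to intervention-arm participants, since controls attend no workshop before week 12.
- For each primary activPAL variable, name one deciding group contrast, for example the average of weeks 4 and 12. How the three variables share alpha is a separate decision that this change does not settle.
- Delete the 2 × 3 ANOVA or label it a sensitivity analysis, and use the same model for the secondary outcomes.
- Restate power for the chosen contrast over a range of ICC.

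Optional, and to be checked by simulation first: the small-sample degrees-of-freedom method, the pooling rule across imputations, how workshop enters the imputation model, and age (the blocking factor) as a covariate. These choices matter. In one simulated setting (80 randomised, 20% missing both post visits, 10 imputations, ICC 0–0.10), small-sample pooling gave type I error of 2–4% and power of 45–77%. Large-sample pooling gave 3.5–6% and 69–85%.

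The cost is SAP wording and some modelling work, with no new data. With about four workshops, nominal power falls below that of the ANOVA change contrast at a baseline-adjusted ICC of about 0.05 or more (62% against 71% at 0.10 with 64 analysed). More workshops would reduce the loss, but the protocol offers them only if the year-one recruitment target of 60 is missed.
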